### **10.3.2 Intensity of Adverse Events**

The intensity of adverse changes in physical signs or symptoms will be graded according to the CTCAE version 4.03. For all other adverse events not described in the CTCAE, the intensity will be assessed by the Investigator using the following categories:

**Mild** (Grade 1) – transient or mild discomfort; no limitation in activity; no medical intervention/therapy required.

**Moderate** (Grade 2) – mild to moderate limitation in activity, some assistance may be needed; no or minimal medical intervention/therapy required.

**Severe** (Grade 3) – marked limitation in activity, some assistance usually required; medical intervention/therapy required, hospitalization is possible.

**Life-threatening** (Grade 4) – extreme limitation in activity, significant assistance required; significant medical intervention/therapy required, hospitalization or hospice care probable.

**Death** (Grade 5) – the event resulted in death.

### **10.3.3 Action Taken with Study Drug**

The action the Investigator took with study drug as a result of the event should be recorded as one of the following:

**None** – No action was taken with regard to the study drug as a result of the adverse event.

**Interrupted** – Study drug was stopped due to the adverse event, but was later resumed at the same dose.

**Dose decreased** – The dose of study drug was decreased as a result of the adverse event.

**Permanently discontinued** – The subject was withdrawn from the study due to the adverse event.

Only one item should be chosen. If multiple actions apply, the following “worst case” scenario

hierarchy should be used to determine the preferred entry:

Discontinued > dose decreased > therapy interrupted.

#### **10.3.4 Definition of Outcome**

The outcome of the AE should be recorded as one of the following:

**Resolved without sequelae** – The subject fully recovered from the adverse event with no observable residual effects.

**Resolved with sequelae** – The subject recovered from the adverse event with observable residual effects.

**Not resolved** – The adverse event was present at the time of last observation.

**Death** – The subject died as a result of the adverse event.

### **10.4 Immediately Reportable Events**

#### **10.4.1 Serious Adverse Events**

Serious adverse events (SAE's) must be documented on a SAE Report Form must be emailed to the UFHCC DISC Safety Team within **5 days** of discovery of the event. The original copy of the SAE Report and any email correspondence must be kept within the Trial Master File at the study site. The site investigator is responsible for informing the IRB and/or the Regulatory Authority of the SAE as per local requirements.

Follow-up information will be emailed or faxed to the UFHCC using the SAE Report Form stating that this is a follow-up to the previously reported SAE and giving the date of the original report. Each re-occurrence, complication, or progression of the original event should be reported as a follow-up to that event regardless of when it occurs. The follow-up information should describe whether the event has resolved or continues, if and how it was treated, whether the blind was broken or not (if applicable), and whether the participant continued or withdrew from study participation.

The UFHCC Protocol Development Office (PDO) must also be notified of the SAE by email at [[contact]](mailto:[contact]) within **24 hours** of awareness of the event.

#### **Taiho Reporting Requirements**

All SAEs, as well as events of overdose, medication error, pregnancy (whether serious or non-serious), to Taiho Oncology pharmacovigilance or designee within 24 hours of awareness. SAEs will be reported to Taiho Oncology either by e-mail at [TAS-102\\[contact]](mailto:[contact]) or via fax at [contact]. Any SAE inquiries to Taiho Oncology may be done by hotline phone at [contact]. NOTE: The hotline phone number is for inquiries only; not to report SAEs.

At the time of the annual DSUR (data-lock point), all AEs which led to discontinuation; list of subjects with fatal events; and demographic information for all subjects exposed to TAS-102

#### **10.4.2 Other Events Requiring Immediate Reporting**

All pregnancies, regardless of outcome, must be reported to the UFHCC DISC, including pregnancies that occur in the female partner of a male study subject. All pregnancies must be followed to outcome.

Although overdose (dose variance of >25%) and cancer are not always serious by regulatory definition, these events should also be reported to the DISC in an expedited manner. In case the overdose did not result in any adverse event, the Investigator should report this as “overdose, no adverse event” on the SAE form and provide the intended amount, as well as the actual amount, of drug administered. In the event of overdose or exaggerated response, appropriate supportive measures should be employed. Actual treatment should depend on the severity of the clinical situation and the judgment and experience of the treating physician.

Pregnancies and overdoses should be documented and reported per the SAE reporting guidelines in section 10.4.1 above.

#### **10.5 IND Safety Reports Unrelated to this Trial**

*IND safety reports not occurring on this trial but involving the study intervention (outside SAEs) received from outside sources will be forwarded to participating sites for submission to their Institutional Review Boards per their guidelines.*

### **11. STATISTICAL METHODS**

#### **11.1 Sample Size Determination**

This is a pilot phase II study, so we are interested in evaluating the feasibility and safety of a regimen of daily TAS-102 administered to subjects with squamous cell lung cancer. To minimize the number of subjects exposed, the sample size will be determined by the anticipated response rate. A response rate of 20% or above to TAS-102 will be of interest in subjects with previously-treated squamous cell lung cancer. Initially, 14 subjects will be evaluated for response, and if none of the 14 evaluable subjects experiences a partial or complete response, then the study will be terminated. If the true response rate is 20%, the chance of rejection error is less than 5%. However, in the event of one response among the first 14 subjects, further accrual will continue to a total of 30 evaluable subjects to estimate the response rate more precisely with a standard error of no more than 9%. A subject is considered eligible for toxicity evaluation if they have received at least one dose of TAS-102. A subject will be considered eligible for evaluation of activity if they have also received two cycles of therapy as planned.

Based upon the numbers of subjects seen at the University of Florida Cancer Center clinics and our accrual to other similar studies, it is estimated that accrual to the first level (14 subjects) will be completed within nine months. If the study is fully accrued (30 subjects) and at least the last such subject derives benefit from the anticipated maximal number of six cycles, then the length of the entire study will be approximately 24 months.

### **11.2 Analysis of Endpoints/Efficacy**

The primary endpoint to this study will be to document the objective rate of response by RECIST Criteria, version 1.1 of the participants in this trial which will be estimated along with exact 95% binomial confidence intervals.

The secondary endpoints of this study will be to determine the rate of development of toxicities, and the reversibility of toxicities of this regimen; the Objective Response Rate (by RECIST Criteria); the Clinical Benefit Rate (objective response + disease stability rate); the median duration of response in months, and the median Overall Survival.

A secondary endpoint of this study will be progression-free survival following TAS-102 therapy. Kaplan-Meier mean estimates and survival curves of progression-free survival rates will be calculated. Secondary endpoints include clinical benefit rate (CR + PR + SD), toxicities and reversibility of toxicities) will also be estimated along with exact 95% binomial confidence intervals.

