### 2.2 Secondary

- To evaluate the qualitative and quantitative toxicities, and reversibility of toxicities, of this treatment by NCI CTC Version 4.0.3 criteria
- To determine the progression-free survival, in months, of subjects receiving TAS-102 for the treatment of unresectable or metastatic recurrent squamous cell lung cancers
- To determine the percentage of subjects who derive clinical benefit (objective response + stable disease)
- To determine the median duration of responses in months
- To determine the overall survival in months

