## 7.5 **Follow up/Survival**

Patients will be seen in follow-up at least every three months for the first three years after the initiation of therapy, or the date of death, whichever occurs first. Patients who are alive after three years will have follow up every six months for years four and five, then annual follow ups until date of death, or lost to follow up. Those patients who are lost to follow up will have every effort by telephone and mail to contact them for at least one month past their first missed clinic visit, with at least four documented attempts at contact to be made during that time.

Evaluation will consist of an interim medical history and a physical examination. Additional studies, such as labs (CBC and CMP), and any X-rays, or CT, PET/CT, bone scans or MRI scans used in evaluation of response will be repeated as clinically indicated. Other studies, such as, biopsies, will be performed as clinically indicated.

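### Section 11.2 summarises PFS only by a Kaplan-Meier mean with no truncation time, data cut or interval, so the figure depends on the cut date when the longest time is censored

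*Combined protocol and SAP*

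**What the plan says.** The secondary objective in section 2.2 is "To determine the progression-free survival, in months, of subjects receiving TAS-102"; it gives the unit but not the summary statistic. The statistic appears only in section 11.2: "Kaplan-Meier mean estimates and survival curves of progression-free survival rates will be calculated". The paragraph before it names "the median duration of response in months, and the median Overall Survival", so PFS is the one time-to-event endpoint given a mean.

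The exact binomial intervals in section 11.2 are attached to response, clinical benefit and toxicity, not to PFS. I found no truncation time for the mean, no PFS data cut and no PFS interval in the available text.

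Three other places bear on whether patients can still be progression-free when the data are analysed:
- Section 5.1 puts no cap on the number of cycles.
- Section 7.5 follows patients at set intervals for five years, "then annual follow ups until date of death, or lost to follow up".
- Section 11.1 expects the whole study to last about 24 months, and the synopsis about 30 months.

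**The concern.** A Kaplan-Meier mean is the area under the curve. If the patient with the longest follow-up has progressed or died, the curve reaches zero and the area is fully determined. If that patient is censored, the curve stops above zero and the area is complete only up to that time. The result is then a restricted mean whose limit was set by enrolment dates and by the day the database was cut, not by the plan.

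Two analysts working from the same protocol with cuts six months apart could therefore report different PFS figures, each correctly following section 11.2. The trial's answer to the PFS objective would have no fixed definition and no stated uncertainty.

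**Working it through.** **The plan's own figures.** The documents state no PFS figure to reproduce. The design figures around it check out:
- Under the section 11.1 rule, "if none of the 14 evaluable subjects experiences a partial or complete response, then the study will be terminated". At a true response rate of 20% the chance of this is 0.80^14 = 0.044, below the stated 5%.
- Accrual of 14 patients in nine months gives 30/(14/9) = 19.3 months for 30 patients. Six 28-day cycles add 168 days, or 5.5 months. The total is 24.8 months, consistent with the stated 24 or so.

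With accrual over about 19 months and a cut at 24 to 30 months, late enrollees have only about 5 to 11 months of follow-up.

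**Formula.** With ordered times t(1), t(2), … up to t(max), the Kaplan-Meier mean is the sum of S(t(j−1)) × [t(j) − t(j−1)], starting from S(0) = 1 and t(0) = 0. If t(max) is censored, each further month of follow-up for that patient adds S(t(max)) months to the mean. The median is the first time at which S(t) ≤ 0.5.

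**Fixed example.** Take 30 patients: 27 events placed on an exponential curve with median 3 months (assumed), and the last three still progression-free at staggered times. After 27 events S = 3/30 = 0.10, so six more months of follow-up add 6 × 0.10 = 0.60 month.
- Longest censored time 18, 24 and 30 months: mean 4.70, 5.30 and 5.90 months. The median is 2.86 throughout.
- With only one ongoing patient, S = 1/30 and six months add 0.20: mean 4.29, 4.49 and 4.69 months.

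**Simulation.** Inputs: 30 patients (section 11.1), uniform accrual over 19.3 months (derived above), cuts at 24 and 30 months (section 11.1 and synopsis), at least 3,000 trials per scenario. The PFS distributions are assumptions. Repeat runs agreed to within about 0.1 month and one or two percentage points.

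| Assumed PFS | Last time censored, 24 / 30 months | Average KM mean (months), 24 / 30 months | Average KM median (months) |
|---|---|---|---|
| Exponential, median 3 months | 32% / 23% | 4.24 / 4.28 | 2.9 |
| As above, but 10% with median 12 months | 57% / 52% | 5.0 / 5.2 | 3.3 |
| As above, but 10% with median 36 months | 75% / 78% | 5.5 / 5.9 | 3.4 |

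Averaged over trials, the median moves by less than 0.01 month between the cuts in all three rows.

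Averages hide part of the shift within a single trial. In the first row the mean absolute change from the 24- to the 30-month cut is 0.14 month.

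**Range over other assumptions.** With exponential PFS of median 2, 3, 4 and 6 months, the last time is censored in 19%, 32%, 47% and 69% of trials at 24 months. The mean absolute shift to a 42-month cut is 0.06, 0.18, 0.33 and 0.73 month. With 15% of patients at a median of 24 months and the rest at 2 to 6 months, that shift is 1.1 to 1.6 months.

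**The case against.** The strongest reply is that the effect is small where the documents point. Section 1.1 puts overall survival with untargeted salvage agents at about 6 months, so PFS is likely to be short. With a 3-month exponential the average mean moves by 0.04 month between the planned cuts, against a between-trial standard deviation of about 0.8. Even with a 36-month subgroup the move of about 0.4 is well inside a standard deviation of 1.2 to 1.3. This stands, and it limits the size of the point.

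A second reply is that the word mean is a slip for median, and that the planned curves would let a reader take off the median and landmark rates. The slip is plausible, given the neighbouring medians. But the text in force says mean, and changing the statistic after the data are seen would be a departure from the plan. A curve also does not fix which figure is reported, or its interval.

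Three stronger readings are tempting and are not supported:
- **That the PFS figure is generally unstable.** A drift from 5.5 to 7.2 months does appear in simulation, but it needs both a 10% subgroup with a 36-month median and a 60-month cut. The documents give no basis for such a subgroup and plan a study of 24 to 30 months.
- **That the gap between mean and median shows the fault.** An exponential with median 3 months has a true mean of 3/ln 2 = 4.33 months, so an estimate near 4.3 is on target. The mean is a different summary, not a biased one.
- **That the mean will be set against published median PFS.** The documents cite no published PFS value and set no PFS benchmark. The historical comparison in section 11.3 sits under demographic and baseline characteristics.

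**Conclusion.** The point holds in a limited form. Section 11.2 names a PFS summary whose value depends on the cut date whenever the longest time is censored, and nothing else in the plan fixes the limit.

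Under the assumed distributions tabulated above, that condition arises in roughly a quarter to a third of trials with short exponential PFS, and in about 50 to 80% if a tenth of patients do much better. The resulting move in the average between the planned cuts runs from under 0.1 month to about 0.4 month. Longer follow-up increases it. These sizes rest on PFS distributions that the documents do not supply; the mechanism and the missing specification do not.

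PFS is a secondary, descriptive endpoint. The response-rate analysis and the 14/30 rule are untouched. It should be corrected, but it does not threaten the trial's main conclusion.

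**What to change.** In section 11.2, replace the Kaplan-Meier mean with the Kaplan-Meier median PFS and its 95% confidence interval, in line with duration of response and overall survival. PFS rates at a few pre-stated landmark times, with confidence intervals, would be a useful option.

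If a mean is preferred, call it a restricted mean and fix its truncation time before any data are examined. The choice matters: for exponential PFS of median 3 months (assumed), the restricted mean (3/ln 2) × (1 − 2^(−h/3)) is 3.25 months at a horizon of h = 6 months, 3.79 at 9 and 4.06 at 12.

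The cost is one sentence of analysis text. It needs no extra data, visits or patients.

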### **11.3 Analysis of Demographic and Baseline Characteristic**

The analysis of demographic characteristics (age, gender, tobacco abuse history and ethnicity) and baseline characteristics, including weight change, performance status, and histologic subtype, will be primarily descriptive. However, they will be compared between the treatment arm and historical controls to determine if there is any imbalance, which might skew the results of the patient outcomes. These endpoints will be primarily descriptive in nature due to the small patient numbers; however, these results will be compared against historical US controls. Continuous variables will be compared to historical controls using either a two-sample t-test or Wilcoxon rank sum test depending on normality assumptions, and discrete outcomes will be compared using either Chi-square or Fisher's exact tests.

### **11.4 Analysis of Safety Data**

Patients will be examined and graded each cycle for subjective/objective evidence of developing toxicity according to NCI-CTC version 4.03 toxicity criteria. Incidence tables will be generated to summarize incidence of patients reporting at least one episode of each specific adverse event, incidence of adverse events causing withdrawal, and incidence of serious adverse events. Patients will have laboratory values assessed weekly during the first cycle, and in the absence of grade 3 or 4 toxicity, will subsequently have laboratory monitoring every cycle from cycle 2 onward. In the absence of significant treatment-related abnormalities, in subsequent courses patients will not require weekly laboratory evaluation, but will require the documentation of return to baseline values prior to the initiation of subsequent courses of therapy. All patients experiencing toxicities

will require the documentation of return to baseline values prior to the initiation of subsequent courses of therapy.

All patients who received study drug will be included in the safety analysis of this combination regimen. Adverse event data and corresponding toxicity grades during treatment and during long-term follow-up will be summarized in the form of tables. Incidence tables will be generated to summarize incidence of patients reporting at least one episode of each specific adverse event, incidence of adverse events causing withdrawal and incidence of serious adverse events. The total number of episodes for each event reported (Frequency Table), the severity and attribution to study therapy of each episode reported (Severity Table and Attribution Table) will also be displayed. Listings of adverse events by patients will include the time to onset, the duration of each event, the severity of each event, and the relationship of the event to study therapy, whether it was a serious event, and whether it caused withdrawal. Safety data will be summarized for the overall patient group and by dose levels. Dose-toxicity curves will be fitted to the final data to estimate the toxicity rates of each dose levels.

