### 5.3 Dose Modifications

The National Cancer Institute (NCI) Common Toxicity Criteria for Adverse Events Version 4 (CTCAE) will be used to grade toxicity (<http://evs.nci.nih.gov/ftp1/CTCAE/About.html>).

The starting dose of TAS-102 is 35 mg/m^2 up to a maximum of 80 mg per dose (based on the trifluridine component) orally twice daily within one hour of completion of morning and evening meals on Days 1 through 5 and Days 8 through 12 of each 28-day cycle until disease progression or unacceptable toxicity. Doses will be rounded to the nearest 5 mg increment. Study medication will be administered on a 4 week schedule. Doses will be delayed or reduced for clinically significant (Grade 3-4) hematologic and non-hematologic toxicities that are related to protocol therapy according to the guidelines shown in the Dose Delays/Dose Modifications table that follows. Dose modifications will follow predefined dose levels. Dose adjustments for hematologic toxicity are based on the blood counts obtained in preparation for the day of treatment.

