#### 5.3.1 Dose Modification Table

Dose level 0 (standard starting dose)	35 mg/m  po bid
Dose level – 1	30 mg/m  po bid
Dose level – 2	25 mg/m  po bid

Inpatient dose reduction and dose interruption will be permitted once a patient has experienced drug-related toxicity provided that the criteria for patient withdrawal from study treatment have not been met. All inpatient dose reductions are relative to the lowest dose of the current cycle.

For all toxicities, doses of TAS-102 will be modified based upon Day 1 and Day 15, complete blood cell counts. Day 1 TAS-102 dosing for each cycle will be held until:

- Absolute neutrophil count (ANC) is greater than or equal to 1,500/mm^3 or febrile neutropenia is resolved

- Platelets are greater than or equal to 75,000/mm^3
- Grade 3 or 4 non-hematological adverse reactions are resolved to Grade 0 or 1

Within a treatment cycle, TAS-102 will be withheld for any of the following:

- Absolute neutrophil count (ANC) less than 500/mm^3 or febrile neutropenia
- Platelets less than 50,000/mm^3
- Grade 3 or 4 non-hematological adverse reactions

After recovery, resume TAS-102 after reducing the dose by 5 mg/m^2/dose (as above) from the previous dose level, if the following occur:

- Febrile neutropenia
- Uncomplicated Grade 4 neutropenia (which has recovered to greater than or equal to 1,500/mm^3, or baseline in subjects with benign ethnic neutropenia) or thrombocytopenia (which has recovered to greater than or equal to 75,000/mm^3) that results in more than 1-week delay in start of next cycle
- Non-hematologic Grade 3 or Grade 4 adverse reaction except for Grade 3 nausea and/or vomiting controlled by antiemetic therapy or Grade 3 diarrhea responsive to antidiarrheal medication

If a subject experiences more than one toxicity, dose reduction should be according to the toxicity with the highest grade. In the case of two or more toxicities of the same grade, the investigator may dose reduce according to that deemed most causally related to study treatment. If more than 3 dose reductions are required, TAS-102 will be discontinued. Do not escalate dose after it has been reduced.

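### The planned dose-toxicity curves compare dose levels that patients reach only through their own earlier toxicity, so the curve can mislead, and 30 patients are too few to correct it

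*Combined protocol and SAP*

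**What the plan says.** Section 11.4 (Analysis of Safety Data) commits to two by-level outputs: "Safety data will be summarized for the overall patient group and by dose levels", and then "Dose-toxicity curves will be fitted to the final data to estimate the toxicity rates of each dose levels". For its tables, the same section counts patients: "Incidence tables will be generated to summarize incidence of patients reporting at least one episode of each specific adverse event". For the curve it gives no model, no counting unit, no rule for assigning events or exposure to a level, and no handling of dose changes caused by toxicity.

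The dosing rules are in Section 5.3. All patients begin at level 0 (35 mg/m² twice daily), and levels -1 and -2 are the listed reductions. Section 5.3.1 gives the route down: "Inpatient dose reduction and dose interruption will be permitted once a patient has experienced drug-related toxicity". It also closes the route back: "Do not escalate dose after it has been reduced". Section 6.4 opens no lower-dose cohort; if level 0 proves intolerable in the first six patients, the trial stops. Section 3.1 caps enrolment at 30.

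**The concern.** A dose-toxicity curve is informative when patients are assigned to doses independently of how they tolerate the drug, as in a dose-finding trial. Here the dose a patient is on is a consequence of that patient's earlier toxicity. Level -1 contains only patients who have already had a reduction-triggering event, and the later cycles at level 0 contain only those who have not. A crude comparison of levels mixes the effect of dose with differences in susceptibility.

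Because the counting unit is left open, the distortion can go either way. Pooling cycles makes lower doses look too toxic when patients differ in susceptibility. Counting patients with any event makes lower doses look too safe when patients do not differ, because fewer cycles remain after a reduction.

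Toxicity is a secondary objective (Section 2.2), and the plan describes the output as an estimate of the toxicity rate at each level. A reader would take it as evidence on whether reducing the dose helps.

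**Working it through.** **Plan's own figures.** The documents give no precision or sample-size figure for the curves. The design figure in Section 11.1 concerns response and reproduces: the chance of no responses in 14 at a true rate of 20% is 0.8^14 = 4.4%, below 5%. It is not at issue.

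**Inputs from the documents.** At most 30 patients (Section 3.1), or 14 if stage 1 stops the trial; an anticipated maximum of six cycles (Section 11.1); one starting level, reduction only after toxicity, no re-escalation (Section 5.3.1).

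**Assumed inputs.** Per-cycle risk p0 of reduction-triggering toxicity for the median patient at level 0: 25%, range 10% to 40%. Between-patient SD on the log-odds scale: 0 to 1.5. True effect d of each level reduction: 0 or 0.5 log-odds. Cycles: uniform on 2 to 6, with 1 to 6 as a check.

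**Model.** logit(p) = logit(p0) + u - d × (levels below 0), with u ~ N(0, SD²). The dose falls one level after each triggering toxicity. Level -1 is the lowest level, and treatment stops at toxicity there. 200,000 simulated patients per scenario.

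**1. Crude per-cycle rates, level 0 / level -1**

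| SD | No dose effect | True 0.5 reduction | 30-patient trials where level -1 looks at least as toxic despite the true reduction |
|---|---|---|---|
| 0 | 25% / 25% | 25% / 17% | 16% |
| 0.5 | 25% / 28% | 25% / 19% | 26% |
| 1 | 24% / 33% | 24% / 25% | 49% |
| 1.5 | 24% / 39% | 24% / 31% | 74% |

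When SD > 0, 25% is the median patient's risk, not the population mean. At SD 1 the true population rates under the 0.5 reduction are 28.6% and 20.7%. The crude 24% and 25% understate level 0 and overstate level -1, because susceptible patients leave level 0.

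**2. Patients with at least one event, by dose at onset; no dose effect, SD 0 (exact).** With q = 1 - p = 0.75 and n = 2 to 6 cycles:
- Level 0: mean of (1 - q^n) = 0.657.
- Level -1: Σ[(1 - q^(n-1)) - (n-1)·p·q^(n-1)] / Σ[1 - q^(n-1)] = 1.3137 / 2.7119 = 0.484.

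So 66% against 48% appears with no dose effect and identical patients. The pairs are 34% / 22% at p = 10% and 83% / 68% at p = 40%. With between-patient variation the gap narrows and then turns: 63% / 59% at SD 1 and 61% / 65% at SD 1.5.

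**3. Events that trigger no reduction** (for example recovered Grade 1 to 3 myelosuppression, Section 5.3.3). Assumed baseline 35%, SD 1, true 0.5 reduction. Level 0 / level -1 is 37% / 28% at correlation 0 with the trigger (unbiased), 35% / 31% at 0.5, and 33% / 33% at 1.

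**4. Does sample size cure it?** A separate simulation used three levels, 75% of patients continuing to each next cycle, baseline log-odds -1, SD 1.5 and d = 0.5. True rates were 33%, 25% and 19%; crude rates averaged 27%, 31% and 37%. The unadjusted slope had the wrong sign in 65% of trials at N = 30 and 97% at N = 300. This is bias, which more patients do not remove.

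**5. Can it be adjusted at 30?** A random-intercept logistic model with a true effect of 0.5 and SD 1 (1,000 replicates) gave:
- one reduction allowed: median 0.57, central 95% of estimates -0.77 to 2.58, sign wrong or zero in 21%;
- two allowed: median 0.53, -0.44 to 2.08, sign wrong or zero in 17%.

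In the step 4 set-up the same kind of model at N = 300 gave a median of 0.50 (0.14 to 0.79). The method works in principle; 30 patients do not support it.

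**6. How much data each level could hold.** Over trigger rates of 10% to 40% and SD 0 to 1.5, about 8 to 22 of 30 patients reach level -1 with 2 to 6 cycles, and 4 to 16 with 2 to 3 cycles. Level -2, if used at all, holds 1 to 11 and 0 to 4 respectively. Whether it can be used is unclear. Section 5.3.1 lists two reduced levels but says "If more than 3 dose reductions are required, TAS-102 will be discontinued". Section 5.3.3 reduces again on recurrence, yet takes patients who need two reductions off study.

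**The case against.** The best case against this is about size and scope.

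- **The base rate looks high.** A 25% per-cycle risk means about 66% of patients have a triggering event. Section 9.1.9 gives 69.3% with any Grade 3 or worse event, and many of those would not trigger a reduction. This stands, but at 10% with SD 1 and a true 0.5 reduction the crude rates are still reversed, at 11.6% and 13.3%. The lower rate mainly cuts the patients at level -1, from about 16 to 9.
- **A minimum of two cycles is too generous**, since one dose suffices for toxicity evaluation (Section 11.1). This also stands. With 1 to 6 cycles, level -1 holds about 13 patients in the base case, and the per-patient contrast with no dose effect becomes 57% / 59% at SD 1. At SD 0 the spurious fall remains: level 0 drops to 59%, and level -1 stays at 48% because one-cycle patients never reach it. The per-cycle bias persists.
- **Most adverse events are low grade and trigger no reduction.** True, and step 3 shows that the bias is then small unless such events track the trigger closely.
- **The between-patient SD has no source and the direction is undetermined.** True. The percentages illustrate what can happen and do not predict it.
- **An adjusted estimate with its interval could be reported instead of deleting the curve.** Possible, but no such model is planned, and estimates that take the wrong sign or zero in roughly one trial in five would inform nobody.
- **Safety reporting in all treated patients and exact intervals are already planned.** That makes the remedy cheap; it does not make the curve sound.

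**Conclusion.** The concern holds. By the protocol's own rules, dose level depends on earlier toxicity, so the curve in Section 11.4, fitted without adjustment, does not estimate the toxicity rate of each dose. That structural point needs no assumed inputs.

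The size does. Pooled per cycle, there is no bias if patients are equally susceptible. At a between-patient SD of about 1 a true 0.5 log-odds benefit is hidden, and at 1.5 it is reversed. Counted per patient, a fall from 66% to 48% can appear with no dose effect at all. These figures rest on assumed trigger rates, cycle numbers and SDs, and apply mainly to toxicity that triggers a reduction.

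The consequence is confined to one secondary safety output. The response endpoint, sample size, stopping rules and overall toxicity tables are untouched. It should still be changed, because following the plan as written can produce a wrong statement about dose.

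**What to change.** 1. Delete the dose-toxicity-curve sentence from Section 11.4.
2. Report toxicity in all treated patients with the exact 95% intervals already planned in Section 11.2, described as the rate for treatment started at level 0 with protocol dose reductions, not as the rate at level 0. With 30 patients, 11 events would give 37% (20% to 56%) and 6 would give 20% (8% to 39%): wide, but free of selection by earlier toxicity.
3. Label any by-level summary as descriptive, by dose at onset, conditional on prior toxicity, and not comparable with level 0.
4. Optionally, add dose at onset to the adverse event listing. Section 10.3.3 already records per event whether the dose was decreased.
5. Separately, reconcile Sections 5.3.1 and 5.3.3 on the number of reductions, so that it is known which levels can hold data. No view is taken here on which rule should stand.

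For items 1 to 3 the cost is one deleted sentence and two labels. What is lost is a figure that could not have been interpreted.
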